10.2.3 Subgroup and adjusted analyses

Subgroup analyses are planned to explore between-group difference in the impact of KMC compared to standard of care on mortality, by GA (<28, 28-32, or >32 weeks), birthweight (<1000, 1000-1499, or ≥ 1500 g), hospital site, and level of predicted mortality risk based on the NMR-2000 score [high (≤ 16), medium (17-22), low (≥ 23)]. A paediatrician or medical research officer will conduct a Ballard examination to determine GA (27). GA is an important predictor of newborn survival. In settings with specialised neonatal care without intensive care, such as the five recruitment sites, neonatal mortality rates are 86% in neonates born at <28 weeks and 41% in neonates born at 28 to 31 weeks (51). The NMR-2000 is a simplified score to predict in-hospital mortality among neonates ≤ 2000 g, which has been validated in the UK and The Gambia (69). NMR-2000 uses data on three parameters (birthweight, SpO₂ at admission, highest level of respiratory support at any point within 24 hours of birth), which are already being collected on enrolled neonates.

Further exploratory analyses will be carried out to explore the association between mortality and time of initiation (<12, 12-<24, or ≥24 hours), and continuity of KMC (median hours per day: <6, 6-<12, 12-<18, or 18-24 hours).

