4.2 Eligibility Criteria for the Trial

Participants must meet the following inclusion criteria and not have any of the exclusion critieria to be able to participate in the trial.

4.2.1 *Inclusion criteria*

- Neonate admitted to JH, MH, EH, IH, or KNRH (inborn or outborn)
- Singleton, twin, or triplet (if triplet pregnancy resulted in demise/stillbirth of one or more fetuses)
- Birthweight $\geq 700\text{g}$ and $\leq 2000\text{g}$
- Chronological age 1-48 hours at time of screening
- Alive at time of recruitment
- Parent/caregiver able and willing to provide KMC
- Parent/caregiver willing to attend follow-up visit
- Indication for KMC “uncertain” according to WHO guideline concerning clinical stability: pragmatically defined as receiving ≥ 1 therapy: oxygen, CPAP, IV fluids, therapeutic antibiotics, phenobarbital

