5.5 Collection of Baseline Data

5.5.1 Clinical data

Study staff will collect the following clinical data as soon as possible after enrolment, with the exception of gestational age assessment and length measurement, which may be delayed to within 48h of admission. If any medical therapies (e.g., oxygen) have already been started by study staff, these will be continued throughout the clinical data collection process.

Research staff will be trained in appropriate infection control procedures and study specific protocols will detail infection control measures for the use of study equipment (pulse oximeters, weighing scales, etc.) to avoid cross-infection and contamination between participants.

- Axillary temperature will be measured with a digital thermometer (in degrees Celsius). Three measurements will be taken to enable calculation of the mean value.
- A capillary sample for blood glucose measurement will be obtained by heel prick using appropriately sized lancets and study-specific blood glucose machines at each site.
- Physical examination will be conducted.
- Head circumference [occipitofrontal circumference (OFC)] will be measured. • Gestational age will be estimated using the Ballard score (Appendix C)
- Crown-foot length will be measured.

The collection of baseline clinical data is estimated to take approximately 30 minutes, not including gestational age and length measurement. Data will be recorded in the eCRF (Appendix D) by trained study staff.

5.5.2 *Sociodemographic data*

Following the collection of baseline clinical data (with exception of gestational age and length measurement), trained study staff will collect the following sociodemographic data using standardised parent interviews and medical records (antenatal and hospital). Data will be recorded in the eCRF by trained study staff.

- Maternal details: contact details; date of birth; marital status; employment; highest level of education; date of last menstrual period (LMP); significant medical history; antenatal history (gravidity, parity, complications, interventions)
- Perinatal details: mode of delivery; presence of sepsis risk factors; administration of antenatal steroids and antibiotics in preceding 7d; APGAR scores; date and time of birth
- Neonatal details: gender; age at admission; admission diagnoses; multiple birth; interventions since birth (resuscitation, medications, other therapies)

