participants when they return for follow-up. Peer counselling will address many maternal concerns and may help facilitate longer durations of KMC. A related RCT demonstrated the efficacy of peer counselling in promoting breastfeeding amongst hospitalised neonates (97). We will also engage hospital administrators about KMC guidelines. Adjustable beds and KMC wraps will be provided, as these have been shown to improve adherence (98). Increased space is being organised for the JH and MH newborn units for KMC beds/chairs and existing incubators.

18. Significance of the Proposed Work

Globally, there are an estimated 2.5 million neonatal deaths each year (15), among which >80% occur in neonates who are small at birth, due to being preterm and/or SGA (16). Major mortality reductions could be achieved by improving care of small neonates in low-resource settings (16–18). WHO guidelines recommend KMC for “routine care of newborns weighing $\leq 2000\text{g}$... initiated as soon as newborns are clinically stable” (8), where stability has been defined as vital functions (breathing, circulation) not requiring “continuous medical support and monitoring,” and not being “subject to rapid and unexpected deterioration” (3). However, estimates suggest that $\geq 75\%$ of neonatal deaths occur before stabilisation in settings without intensive care (16,17,22). Further, over three-quarters of neonates in sub-Saharan Africa and south Asia lack access to intensive care (99). The only RCT of KMC in neonates before stabilisation with mortality outcomes was conducted in Ethiopia (123 neonates $\leq 2000\text{g}$). It reported a 43% reduction in mortality (RR 0.57); yet, 66% of deaths and the major difference between arms occurred within 12 hours of birth (18,23). In addition, this RCT excluded $>50\%$ of eligible neonates, did not utilise allocation concealment, and had an apparent group imbalance at baseline (favouring KMC) (23), compromising robustness (18,100). Thus, the effect of KMC initiated before stabilisation in hospitals without neonatal intensive care remains a research priority, still not being addressed, and a well-designed RCT is warranted to examine mortality impact in non-intensive care settings (18).

19. Publication and Dissemination Plan

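### The NMR-2000 mortality subgroup counts respiratory support up to 24 h of age, which for babies randomised earlier includes care given after allocation

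*Protocol*

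**What the plan says.** Section 10.2.3 of the protocol states: "Subgroup analyses are planned to explore between-group difference in the impact of KMC compared to standard of care on mortality". Four variables are named: gestational age, birthweight, hospital site and "level of predicted mortality risk based on the NMR-2000 score", the last in three bands (16 or below, 17 to 22, 23 or above). The score combines birthweight, SpO2 at admission and the "highest level of respiratory support at any point within 24 hours of birth". That window runs from birth, and nothing in the section ends it at randomisation.

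The inclusion criterion in section 4.2.1 is "Chronological age 1-48 hours at time of screening". Section 5.6 places randomisation after the necessary baseline data and before allocated care begins, and section 5.7.1 has KMC start as soon as it can after that. Under section 6.1.3, CPAP may be started on deterioration where it is local standard of care.

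Gestational age comes from the Ballard examination. Section 5.5.1 asks for clinical data soon after enrolment, "with the exception of gestational age assessment and length measurement, which may be delayed to within 48h of admission". The 30-minute estimate for baseline collection also leaves it out. The screening list in section 5.2 does not include gestational age, and section 5.6 does not name it among the data needed before randomisation. Section 5.5.2 does collect the date of the last menstrual period.

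**The concern.** A subgroup variable should be settled before allocation, so that the babies compared within a subgroup differ only by arm and chance. The respiratory component of NMR-2000 does not meet that condition for babies randomised before 24 h of age. Section 2.1 lists cardio-respiratory stabilisation among the pathways by which KMC is thought to work, and section 6.3.1 makes cardio-respiratory stability in the first 24 h after randomisation a process outcome. Section 3.2.6 leaves bubble CPAP to the on-duty paediatrician, who will see whether the baby is skin-to-skin. Death before 24 h also shortens the time in which support can be stepped up.

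If allocation changes recorded support, babies of a given prognosis fall into different risk bands in the two arms. An apparent difference in effect between bands can then arise where there is none. Readers would use this subgroup to judge which babies gain or lose from KMC before stabilisation.

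The issue with gestational age is different and smaller. The trait is set at birth, but its measurement may come after allocation is known, or may never happen if the baby dies first.

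**Working it through.** The plan gives no figure on this point, so there is none to reproduce. The timing follows from the text; the sizes below are illustrations.

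**Timing.** For a baby randomised at age *t* hours, max(0, 24 − *t*) hours of the support window fall after allocation: 22 h for *t* = 2, 12 h for *t* = 12, and none for *t* ≥ 24. The component is a maximum, so only an increase after allocation can change it. The protocol does not give the share of babies randomised before 24 h.

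**NMR-2000 illustration.** From the protocol: a true RR of 0.75 (the 25% reduction in section 1.2), applied in every stratum. Assumed: three latent strata among controls.
- A, higher support already reached before randomisation: 25% of babies, mortality 45%.
- B, would step up after randomisation: 20%, mortality 35%.
- C, never steps up: 55%, mortality 15%.

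Overall control mortality is 0.25×0.45 + 0.20×0.35 + 0.55×0.15 = 26.5%. The higher-risk group is everyone who reaches the higher support level; the rest form the lower-risk group. Let KMC multiply the number stepping up by *e* among the share *f* randomised before 24 h, so the overall factor is 1 + *f*(*e* − 1).

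Worked case, *f* = 1 and *e* = 0.7:
- Control, higher: (0.1125 + 0.07)/0.45 = 0.4056. Control, lower: 0.15.
- KMC, higher: 0.75 × (0.1125 + 0.14×0.35)/0.39 = 0.3106, so RR = 0.77.
- KMC, lower: 0.75 × (0.06×0.35 + 0.0825)/0.61 = 0.1273, so RR = 0.85.

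| *f* | *e* | RR, higher-risk | RR, lower-risk |
|---|---|---|---|
| 0 | any | 0.75 | 0.75 |
| 0.5 | 0.7 | 0.76 | 0.80 |
| 0.5 | 1.5 | 0.70 | 0.75 |
| 1 | 0.7 | 0.77 | 0.85 |
| 1 | 1.0 | 0.75 | 0.75 |
| 1 | 1.5 | 0.66 | 0.75 |

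Groups formed from support up to randomisation return 0.75 throughout. The split here is on support alone. The real score also uses birthweight and admission SpO2, which should dilute the effect.

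**Gestational age illustration.** Let *p*₀ and *p*₁ be the true risks and *q*₀ and *q*₁ the shares of deaths that occur before the Ballard. Among babies with a value,

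RR = [*p*₁(1 − *q*₁)/(1 − *p*₁*q*₁)] / [*p*₀(1 − *q*₀)/(1 − *p*₀*q*₀)].

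With *p*₁ = 0.75*p*₀ and *p*₀ of 18% or 25% (the control rates in section 10.1):
- equal shares missed, 10% to 50%: RR 0.72 to 0.75;
- 30% missed in controls and 20% under KMC: 0.82 to 0.83;
- 20% in controls and 30% under KMC: 0.66.

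The direction depends on when the effect occurs. Take *p*₀ = 25% and suppose 66% of control deaths fall within 12 h, so early and late control risks are 16.5% and 8.5%.
- Whole effect early (KMC 10.25% and 8.5%), half of the examinations delayed past 12 h: (13.625/94.875)/(16.75/91.75) = 0.79. All delayed: (8.5/89.75)/(8.5/83.5) = 0.93.
- Same RR early and late (KMC 12.375% and 6.375%), half delayed: (12.5625/93.8125)/(16.75/91.75) = 0.73. All delayed: (6.375/87.625)/(8.5/83.5) = 0.71.

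**The case against.** A reader might infer that two of the four subgroups rest on variables fixed after randomisation and that both sets of results are therefore biased. The documents do not support that. Treatment cannot alter gestational age, and the Ballard may be delayed but need not be. For NMR-2000, the window has closed before allocation for babies randomised at 24 to 48 h. Section 14.5 lets out-of-hours admissions wait until the next morning for assessment, so some babies will be randomised later. Oxygen and CPAP are themselves qualifying therapies under section 4.2.1, so some babies enter with support already recorded, and KMC cannot lower a maximum already reached. Both arms follow the same clinical guidelines. All of this stands and limits the size; none of it ends the window at randomisation.

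A reader might also take it from section 18 that deaths in this trial will cluster in the first hours and so remove babies from the gestational-age subgroup. The statement there, "66% of deaths and the major difference between arms occurred within 12 hours of birth", describes an earlier trial that the protocol criticises on method. Here babies must be alive at recruitment, and those with severe life-threatening instability are excluded, so the 66% cannot be carried over to randomised deaths. The figures of 0.79 and 0.93 also need the whole effect to fall early; a constant RR moves the result slightly the other way.

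A missing-data rule for gestational age may properly sit in an analysis plan that is not shown. That is why it is secondary here. The NMR-2000 window is different, because the protocol itself writes it down.

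**Conclusion.** The concern holds for the NMR-2000 subgroup, as a risk of bias. For babies randomised before 24 h of age, the stated rule lets care after allocation and early death help set the risk label. Under the assumed strata, with KMC changing escalation by a factor of 0.7 to 1.5, a uniform RR of 0.75 appears as 0.66 to 0.77 in the higher-risk group and 0.75 to 0.85 in the lower. With half the babies randomised before 24 h, the ranges are 0.70 to 0.76 and 0.75 to 0.80. No strata, mortality or escalation figures of this kind are in the protocol, and splitting on support alone probably overstates the effect on the three-part score. The bias is nil if randomisation comes after 24 h or KMC leaves recorded support unchanged.

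For gestational age, the risk is of missing values, or of scoring with allocation known. Equal missingness matters little; the direction under unequal missingness is not known in advance.

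These are exploratory subgroups. Birthweight and site are fixed before allocation and are sound, and the primary intention-to-treat comparison is unaffected.

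**What to change.** In section 10.2.3, define the NMR-2000 subgroup from birthweight, admission SpO2 and the highest respiratory support recorded from birth up to randomisation. Keep the full 24 h score as a sensitivity analysis. Section 5.5.2 already records interventions since birth, so the data cost is little more than a time for each change in support. The downside is departure from the validated 24 h score: its cut-points may fit less well, most of all for babies randomised within the first hours.

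For gestational age, use the estimate from the last menstrual period as the fallback for babies without a Ballard, and report missing gestational age by arm. This dating is less precise than the Ballard, but it keeps early deaths in the analysis wherever the date is known. Do not require the Ballard before randomisation where that would delay KMC.

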2.2 Gaps in the Evidence regarding Kangaroo Mother Care

Estimates suggest that $\geq 75\%$ of neonatal deaths occur *prior to stabilisation* in settings without intensive care (16,17,22). A notable gap exists in the evidence supporting the use of KMC in this vulnerable population. The only RCT of KMC in neonates before stabilisation with mortality outcomes was conducted in Ethiopia (123 neonates ≤ 2000 g) and reported major mortality impact [RR 0.57, 95% confidence interval (CI) 0.33-1.00] (4) (23). Notably, this trial excluded $>50\%$ of eligible neonates, did not utilise allocation concealment, and had an apparent imbalance between groups (favouring KMC) at baseline, with a greater proportion of those receiving standard care being born at gestational ages (GA) < 32 weeks or weighing < 1250 g (4,9). Among 17 RCTs (14 enrolled only ‘clinically stable’ neonates) comparing KMC with conventional care in low birthweight (LBW, < 2500 g) neonates aged < 15 days, there was significant variability in how clinical stability was defined. Six defined this based on therapies (28–33), five on ‘hemodynamic stability’ (23,34–37), and three on specific vital sign parameters (38–40), while three provided no definition at all (41–43). Hence codifying stability criteria for KMC is critical. A recent WHO guideline for care of preterm neonates highlighted evidence gaps regarding the effect of KMC on mortality amongst neonates that are not yet stable. These included absence of criteria to

identify which neonates are *stable enough* to safely receive KMC; the optimal time for initiation; and the duration required to reduce mortality (8).

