Finding 2: Monitoring and provision of concurrent care therapies was feasible in the KMC position: To demonstrate the feasibility of monitoring and providing care therapies (oxygen, IV fluids, etc.) in the KMC position, we enrolled a sample of 10 neonates meeting proposed trial eligibility criteria between July and December 2016. Gestational age was determined by Ballard examination (57). Mothers were counselled to provide KMC ≥ 18 h per day. During interruptions when mothers carried out activities like bathing, a family member was encouraged to provide KMC. If none was available, the neonate was placed in an incubator until the mother returned. Neonates were otherwise managed according to unit guidelines. All neonates received continuous monitoring of SpO₂ and HR.

Among the 10 neonates enrolled, median birthweight was 1310g [interquartile range (IQR) 820-1600g], median gestational age was 28 weeks (IQR 26-31 weeks), and median length of stay was 10 days (IQR 9-14 days). Eight neonates were discharged home and two died. Both neonates that died were extremely premature (26-27 weeks) and extremely LBW (700-750g), thus at very high risk of death, particularly in a low-resource setting given the lack of ventilatory support and other intensive care usually required for survival at this gestational age. The median duration of individual KMC episodes ranged from 115 to 134 minutes, and the median daily duration ranged from 4.5 to 9.7 hours, with a slight upward trend over time. Two neonates received the target duration of 18 hours of KMC on day 1 (18.1 and 21.6 hours) and one neonate received the target duration on day 5 (18.3 hours) (see Section 17 for discussion about KMC compliance). The mean number of care therapies received ranged from 3.7 to 4.1 per day across the first 14 days, and the number of therapies a neonate was receiving did not affect the daily duration of KMC. Continuous SpO₂ monitoring was conducted throughout the enrolment period for all participants, and providers did not report any problems with monitoring or care provision.

Finding 3: KMC (prior to stabilisation) and randomisation were acceptable to parents and providers:

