3.2.5 Clinical Stability Criteria

Neonates will be considered stable when the following criteria have been met for a continuous period of at least 24h [criteria consistent with the WHO I-KMC trial (61)]:

- (i) Breathing spontaneously with $\text{SpO}_2 >90\%$ in room air
- (ii) No need for supplemental oxygen or CPAP
- (iii) Respiratory rate 40 to <60 breaths per minute
- (iv) No apnoea
- (v) HR 80 to <180 beats per minute
- (vi) Axillary temperature 36.0 to 37.4 degrees Celsius
- (vii) No need for IV fluids

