5.7.1 Delivering the intervention arm

KMC will be initiated as soon as possible following randomisation. Neonates allocated to the intervention arm will be naked except for hat and diaper. They will be secured to the exposed chest of the mother/caregiver using a KMC wrap. Prior to placing the neonate in the skin-to-skin position, a study nurse or medical officer will attach a pulse oximetry probe to the hand and a temperature probe to the torso. These procedures will take place in the admission area, prior to moving the baby to the study area. On arrival at the study area, the mother/caregiver will be seated on an adjustable bed. If required, oxygen will be provided from a cylinder or concentrator (depending on available resources at each site). Oxygen will be delivered to the neonate via nasal cannula or mask (if CPAP is required). If IV fluids are required, a bag of IV fluids will be hung and an IV cannula will be placed by a study nurse or medical officer. The study nurse or medical officer will then initiate IV fluids, with drip rate calculated according to standardised guidelines. If the mother/caregiver needs to take a short break (e.g., to shower or use the restroom), the neonate will be placed in an incubator or under a radiant heater. Every effort will be made to encourage skin-to-skin contact for 18h/day, unless otherwise clinically indicated. While we anticipate the mother will be the primary KMC provider, a family member or close friend (helper) may also provide skin-to-skin care in order to avoid disruptions. Clinical study staff at each site will counsel mothers/caregivers about KMC throughout the hospital stay, including the time of discharge. In addition, mothers who practised KMC as participants may be engaged as peer-counsellors when they return for follow-up. For each episode of skin-to-skin contact, the caregiver providing KMC (e.g., mother, father, helper) and the time of initiation and duration will be monitored and recorded in the electronic CRF (using bedside tablets).

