5.7.2 Delivering the control arm

Neonates allocated to the control arm will be placed in an incubator or under a radiant heater, as per standard management at the study sites. They will wear a hat and be wrapped as per standard care. Oxygen will be provided from an oxygen cylinder or concentrator and IV fluids will be securely attached via an IV cannula with drip rate calculated, as in the intervention arm. The pulse oximeter will be placed inside the incubator or next to the radiant heater. The parent/caregiver will be able to touch the baby, if

requested, but will not provide any skin-to-skin contact until he/she meets clinical stability criteria (see Section 3.2.5), which are consistent with those used in the WHO I-KMC trial and in line with standard clinical procedures at the study sites. Once stable, the baby can transition to routine (intermittent) KMC with the parent/caregiver in a chair or bed in the study area.

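### Relating mortality to median daily KMC hours builds in a false dose-response, because death and suspension before death cut the hours short; the start-time comparison has a smaller, clock-dependent version of the problem

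*Protocol*

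**What the plan says.** Protocol Section 10.2.3 ends with two comparisons beyond the subgroup analyses: "Further exploratory analyses will be carried out to explore the association between mortality and time of initiation" (<12, 12 to <24, and 24 h or more), and the same for "continuity of KMC (median hours per day: <6, 6-<12, 12-<18, or 18-24 hours". They are called exploratory. The section gives no model, population or time origin, and no rule for babies who die early.

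Other provisions that bear on these exposures:

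- **Recording.** Section 6.1.2 captures skin-to-skin contact as a duration per day.
- **Suspension.** Section 9.1 temporarily withdraws severely unstable babies from KMC. Section 9.2 sets conditions for restarting, including a 24 h period without apnoea needing bag-mask ventilation.
- **Start.** Section 5.7.1: "KMC will be initiated as soon as possible following randomisation". Entry under Section 4.2.1: "Chronological age 1-48 hours at time of screening".
- **Control arm.** Under Section 5.7.2 the caregiver "will not provide any skin-to-skin contact until he/she meets clinical stability criteria". Section 3.2.5: "Neonates will be considered stable when the following criteria have been met for a continuous period of at least 24h".
- **Outcome clock.** The Definitions count early neonatal death on days 0-6 from birth; Section 10.2.2 counts seven days from enrolment.
- **Expected hours.** Section 2.4, from 10 babies: "the median daily duration ranged from 4.5 to 9.7 hours".
- **Purpose.** Section 2.2 lists among the evidence gaps "the optimal time for initiation; and the duration required to reduce mortality".

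**The concern.** Both exposures arise after randomisation and can be observed only while the baby lives. For hours, the causal arrow partly runs backwards: a baby who dies on the first day has had little time to receive KMC, and a deteriorating baby is taken off it. Low hours are then in part a consequence of death or impending death, and longer KMC looks protective even if it does nothing. For start time, a baby must survive to start late.

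These are the analyses that readers would turn to on how early and how long to give KMC, and a gradient favouring longer contact would be read as dose-response. The per-protocol and complier analyses in Section 10.2.4 concern non-adherence. They give no mortality by hours or start time, so they do not repair these comparisons.

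**Working it through.** The plan gives no figure for these analyses to reproduce. The check asks what the stated bands show when KMC has no effect.

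**Inputs from the protocol.** 7-day mortality 25% or 18% (Section 10.1); KMC arm 2188/2 = 1094; daily hours 4.5 to 9.7 (Section 2.4), taken as the mean of intended hours; entry at 1-48 h.

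**Assumptions.** 20% or 40% of deaths fall in the first 24 h. The between-baby SD of intended hours is 4 (mean 9.7) or 3 (mean 4.5), and the day-to-day SD is 2. Hours are unrelated to severity. Days are 24 h periods from KMC start, and the day of death is counted unscaled.

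**1. Mechanism, by hand.** A baby receiving 9.7 h per day evenly, who dies t hours into the first period, records 9.7 × t/24. This is below 6 when t < 6 × 24/9.7 = 14.8 h. With death a fraction f into the second period, the median of two totals is 9.7 × (1 + f)/2, below 6 when f < 0.237, that is t < 29.7 h. Even a baby held without a break cannot record 18 h if it dies within 18 h of starting.

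**2. Hours, no true effect.** Mortality by band at 25% overall:

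| Scenario | <6 | 6-<12 | 12-<18 | 18-24 |
|---|---|---|---|---|
| Mean 9.7, 20% early deaths | 38% | 23% | 18% | 16% |
| Mean 9.7, 40% early deaths | 43% | 21% | 15% | 13% |
| Mean 8, constant hazard (separate model) | 31% | 23% | 18% | 16% |
| Mean 8, front-loaded hazard (separate model) | 37% | 18% | 13% | 12% |

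- In the first two rows the false ratio of lowest to highest band is 38/16 = 2.4 and 43/13 = 3.3.
- Over both mortality levels at mean 9.7, the range is about 28-43% (<6 h) against 8-16% (18-24 h).
- The top band is thin: P(Z > (18 - 9.7)/4) = 0.019, and 0.019 × 1094 is about 21 babies.
- At mean 4.5 it is about 20-29% (<6 h) against 11-19% (6-<12 h).
- A false protective trend is significant in 99-100% of null trials of 1094 babies at mean 9.7, and in 83-100% at mean 4.5.

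**3. Simple repairs for hours.** Scaling to time alive gives 25/24/25/28% (mean 8, constant hazard). Using complete 24 h periods only gives 21.6/20.6/21.3/23.7% (mean 9.7) and leaves out 4-10% of babies. Either removes the part-day artefact. Scaling alone does not deal with suspension: if half of dying babies come off KMC 12 h before death (assumed), the <6 h to 18-24 h ratio is still 1.8-3.4.

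**4. Landmark for hours.** Hours to 48 h, related to later deaths among babies alive at 48 h, give 18.0/17.9/17.9/17.8% (25% mortality, assumed mean 12). With half of dying babies off KMC 12 h or 24 h before death, the ratio is 1.03-1.11 or 1.14-1.27. A 24 h landmark rejects in 3.2-4.6% of null trials.

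**5. Start time, no true effect.** Bands <12 / 12-<24 / 24 h or more, on a birth clock with entry uniform over 1-48 h:

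| Deaths counted | Constant hazard | Front-loaded hazard |
|---|---|---|
| Days 0-6 of age | 24.0/22.7/20.1% | 20.3/17.6/14.2% |
| 7 days from enrolment | 24.7/24.8/24.7% | 20.7/18.6/16.6% |

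- Late-to-early ratios are 20.1/24.0 = 0.84 and 14.2/20.3 = 0.70 by age, and 1.00 and 0.80 from enrolment.
- On a randomisation clock with exponential delay of mean 4 h, exp(-24/4) × 1094 = 2.7 babies fall in the late band. At a mean of 6 h and constant hazard, 5% of null trials reject, the nominal rate.
- If sicker babies start later, the birth-clock ratio ranges over 0.80-1.37.

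**The case against.** The strongest reply is that this is one exploratory sentence. It names no estimator, clock, population or part-day rule; an analysis plan that is not shown may supply them; and the bands are compatible with a landmark analysis. The largest hours gradient also needs the day of death counted unscaled, which the protocol does not say, and complete-day counting brings a significant protective trend down to 1-4% of null trials. Section 9.1 stops KMC for reasons other than severity too, such as an unavailable caregiver. Section 2.2 attributes the evidence gaps to a WHO guideline, and timing and duration are not among the trial's objectives or listed outcomes.

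Much of this stands, and it limits the size and priority of the point. It does not remove it. The protocol itself fixes the outcome, the exposure, the summary (median hours per day) and the cut-points. An analysis plan that applied them to the recorded daily totals would carry the artefact forward, and scaling leaves the part due to suspension. An exploratory label lowers the strength of a claim but does not remove a gradient created by the definition of the exposure.

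A reader might go further and infer that the start-time comparison is biased to the same degree, or in a fixed direction. The documents do not support that: with short delays, or with mortality from enrolment under a constant hazard, the gradient is near nil, and it can reverse. A reader might also infer that control babies will be pooled in, making late starters a group selected for having stabilised. Section 10.2.3 does not say so; it only fails to exclude it.

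**Conclusion.** The point holds for median daily hours. As stated, the exposure is shortened by death and by suspension before death, and under the null it yields a false gradient in favour of longer KMC: about 28-43% against 8-16% at an intended mean of 9.7 h, and about 20-29% against 11-19% at 4.5 h. These sizes rest on the assumed spread of hours, the assumed timing of deaths and an unscaled day of death. The residual ratio of 1.8-3.4 after scaling rests on an assumed rate of stopping 12 h before death. Steeper contrasts follow from higher intended hours, but no such mean is in the documents.

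For start time the problem is real but smaller and conditional on the clock, the outcome origin, the hazard shape and the link with severity.

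A reader might infer that the trial's main conclusions are at risk. They are not: the intention-to-treat analyses, sample size and type I error are untouched. Priority is low to moderate.

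**What to change.** Reword the last paragraph of Section 10.2.3:

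- Restrict both analyses to the KMC arm and name randomisation as the time origin.
- **Hours:** replace the whole-stay median by KMC hours up to a landmark (e.g. 48 h), related to deaths after it among babies alive then, or use a time-updated exposure.
- **Start time:** use a landmark or time-updated exposure only with adjustment for age at randomisation and baseline severity (birthweight, admission SpO2, respiratory support at baseline).
- Label both as non-causal associations.

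The cost is wording only, since birth time, start times and daily durations are already collected. There are two downsides. Deaths before the landmark are left out, so the result describes babies who survive to it. Severity confounding remains, and landmarking does not cure it: if sicker babies start later, an unadjusted 24 h landmark for start time gives a null ratio of 1.6-2.5. Adjusting for severity measured with reliability 0.5 or 0.8 still leaves 1.27-1.62 or 1.10-1.22. The adjustment and the non-causal label are therefore essential parts of the change.
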